- Bleeding causing hypovolemic shock or severe hypotension requiring vasopressors or surgery (BARC type 3b) OR
- Overt source of bleeding with drop in haemoglobin of ≥5 g/dL or whole blood or packed red blood cells (RBCs) transfusion ≥4 units* (BARC type 3b)

Major bleeding (BARC type 3a)

- Overt bleeding plus haemoglobin drop of 3 to <5 g/dL (provided haemoglobin drop is related to bleed); AND
- Does not meet criteria of life-threatening or disabling bleeding.

Minor bleeding (BARC type 2 or 3a, depending on the severity)

• Any bleeding worthy of clinical mention (e.g. access site haematoma) that does not qualify as life-threatening, disabling, or major bleeding.

Technical Success Rate – Technical Success Rate (TSR) is defined as the number of PerQseal® closure devices that are deployed and achieve haemostasis (i.e. cessation of bleeding (excluding cutaneous or subcutaneous oozing)), without need for any alternative treatment (other than manual compression or adjunctive endovascular ballooning) at target access site, divided by the total number of PerQseal® devices where deployment was attempted (as per the PerQseal® closure device IFU). Device malfunction resulting in alternative therapy will be considered as a technical failure.

REVISION	DCN				
AA	2772				
AB	2966				

² Kappetein AP, Head SJ, Généreux P, et al. Updated standardized endpoint definitions for transcatheter aortic valve implantation: the Valve Academic Research Consortium-2 consensus document. *European Journal of Cardio-Thoracic Surgery* 42 (2012) S45–S60.

^{*}Adapted from VARC-22.

^{*}Given one unit of packed RBCs typically will raise haemoglobin concentration by 1 g/dL, an estimated decrease in haemoglobin will be calculated.

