- ix. **Time to Haemostasis** Time to haemostasis (TTH) is determined as the elapsed time from when the Introducer-sheath and PerQseal® closure device have been removed from the patient to first observed cessation of bleeding (excluding cutaneous or subcutaneous oozing) at the target access site arteriotomy.
- x. **Time to Ambulation** Time to Ambulation (TTA) is defined as the time from post procedure sheath removal until the patient is comfortable walking approximately 6 m.
- xi. **Time to Device Deployment** Time to Device Deployment (TTDD) is defined as the time from insertion of the PerQseal[®] closure device into the Introducer-sheath to complete removal of the PerQseal[®] closure device and Introducer-sheath from the patient following deployment.
- xii. **Overall Procedural Time** Overall Procedural Time (OPT) is defined as the time from first invasive contact with the patient's groin to completion of all aseptic procedures related to the groin.
- xiii. **Technical Success Rate** Technical Success Rate (TSR) is defined as the number of PerQseal® closure devices that are deployed and achieve haemostasis (i.e. cessation of bleeding (excluding cutaneous or subcutaneous oozing)) without need for any alternative treatment (other than manual compression or adjunctive endovascular ballooning) at target access site, divided by the total number of PerQseal® closure devices where deployment was attempted (as per the PerQseal® closure device IFU). Device malfunction resulting in alternative therapy will be considered as a technical failure.
- xiv. **Surgical Closure** Standard surgical vascular access and sutured closure.
- xv. **Baseline** Prior to interventional procedure.
- xvi. **Endovascular Aortic/Aneurysm Repair (EVAR)** Endovascular surgery used to treat an abdominal aortic aneurysm (AAA).
- xvii. **Thoracic Endovascular Aortic/Aneurysm Repair (TEVAR)** Endovascular surgery used to treat a Thoracic aortic aneurysm.
- xviii. **Transcatheter Aortic Valve Replacement (TAVR)** Procedure in which a bioprosthetic valve is inserted through a catheter and implanted within the diseased native aortic valve. Also known

as Transcatheter Aortic Valve Implantation (TAVI) or Percutaneous Aortic Valve Replacement (PAVR).

- xix. **Activated Clotting Time (ACT)** Measures the intrinsic clotting activity of whole blood in seconds.

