9.3.1 Subject withdrawal/exclusion

A patient is enrolled in the study by signing an Ethics Committee approved Informed Consent Form; if he/she meets all eligibility criteria (both pre-procedure and during the procedure) and there is intent to close the femoral artery puncture site using the PerQseal® and the PerQseal® closure device contacts the patient¹.

Patients on whom the PerQseal[®] closure device is not used due to failure to meet eligibility criteria/withdrawal of consent are considered not enrolled in the study. Patients not exposed to the PerQseal[®] closure device will not require additional post procedure, pre-discharge or post discharge follow-up assessments and will not be included in safety and performance analyses. For

¹ The PerQSeal® closure device is considered to have contacted the patient if the loading cannula of the PerQSeal® closure device is inserted into the Introducer sheath.

enrolled patients that have received exposure to the PerQseal[®] closure device, but the device was not deployed for reasons other than device failure their data will be included in safety, but not performance analyses and all post procedure, pre-discharge and post discharge follow-up assessments will be performed.

A patient may withdraw from the study at any time if he/she decides to do so. However, all data collected to the time of withdrawal will be recorded in the worksheet, with a note to indicate that the patient has withdrawn their consent to further participate in the study. No further follow-up or data will be recorded for that patient on the worksheet or eCRF. Note that routine management and standard practice of care should continue for the patient without prejudice.

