11. STATISTICAL METHODS

11.1 Analysis populations

All Enrolled subjects (see Section 9.3 Study Population) will be analysed on an Intent-to-Treat (ITT) basis for the Primary and Secondary Endpoint of Safety.

For avoidance of doubt: The ITT analysis population includes all enrolled subjects who undergo attempted access site closure with Vivasure PerQseal® device (i.e. PerQseal® closure device is attempted to be placed into the vasculature and contacted the patient).

All closures from Enrolled subjects will be analysed on a modified Intent-to-Treat (mITT) basis for the Secondary Endpoint of Performance, excluding enrolled subjects which met an exclusion criteria (documented by a protocol deviation).

For avoidance of doubt: The mITT analysis population includes all closures from enrolled subjects who undergo attempted access site closure with Vivasure PerQseal® device (i.e. PerQseal® closure device is attempted to be placed into the vasculature and contacted the patient), with the exception of devices that were prevented from deploying for reasons listed in the exclusion criteria or due to issues associated with the primary procedure.

A secondary analysis population for the primary safety endpoint will include Per-Protocol (PP) for Primary Safety. The PP is a subset of the ITT analysis population with no major protocol deviations and who experienced the safety endpoint or did not prematurely withdraw from the study prior to being evaluated for the primary safety endpoint.

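### The technical success denominator carries an undefined instructions-for-use qualifier that conflicts with the set of closures the SAP tests, and so leaves room to drop failures after the outcome is known

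*SAP*

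**What the plan says.** SAP 4.2, item xiii, takes as numerator the "number of PerQseal® closure devices that are deployed and achieve haemostasis" without alternative treatment other than manual compression or ballooning. It is "divided by the total number of PerQseal® closure devices where deployment was attempted (as per the PerQseal® closure device IFU", after which the bracket closes. The protocol's definition reads "divided by the total number of PerQseal® devices where deployment was attempted (as per the PerQseal® closure device IFU". The reference to the IFU is attached to the denominator only. The SAP adds: "Device malfunction resulting in alternative therapy will be considered as a technical failure".

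Other sections describe the same denominator differently:

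- **SAP 11.1** (mITT): "The mITT analysis population includes all closures from enrolled subjects who undergo attempted access site closure with Vivasure PerQseal® device", provided that contact was made. The section then makes an "exception of devices that were prevented from deploying for reasons listed in the exclusion criteria or due to issues associated with the primary procedure". It also leaves out enrolled subjects who met an exclusion criterion. Departure from the IFU is not among the exceptions.
- **SAP 11.7**: the tested quantity is the proportion of successful closures within the mITT group, with an exact binomial interval compared with 0.81.
- **SAP 9.3.1**: exposed patients whose device was not deployed, for any reason other than device failure, are left out of performance.
- **SAP 11.10**: technical success is assessed in implanted subjects.

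A footnote to SAP 9.3.1 fixes the moment of contact: the device "is considered to have contacted the patient if the loading cannula of the PerQSeal® closure device is inserted into the Introducer sheath".

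**The concern.** Technical success carries its own formal non-inferiority claim, so its denominator should be fixed before any outcome is seen. The bracket can be read as a filter under which a closure that departed from the IFU is not a counted attempt. No section says who would judge that, when, or from what data. The study is unblinded with a single arm, so nothing in the plan prevents the judgement being made after a failure is known. The malfunction sentence keeps malfunctions that lead to alternative therapy as failures, but it does not cover failures put down to operator technique.

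The disagreement goes beyond the bracket. An exposed closure abandoned for a reason of technique is out under 9.3.1, in under 11.1 unless an exclusion criterion or the primary procedure was the cause, and arguably out under 11.10 because nothing was implanted. An analyst could support several different rates from the same data.

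**Working it through.** **Inputs.** Limit 0.81 = 0.84 − 0.03 (SAP 11.7). One-sided level 0.025 and power 0.90 (SAP 10). Exact binomial interval (SAP 11.7). 75 planned subjects (SAP 10), taken here as 75 closures for illustration; bilateral closures would raise this number and mITT exceptions would lower it. The documents give no count of off-IFU attempts, so the counts of 1, 2 and 5 below are assumptions.

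**The plan's own figure.** SAP 10 states a minimum of 44 closures for performance but gives no assumed true success rate, so 44 can only be solved backwards. The smallest n reaching 90% power in an exact test against 0.81 is 58, 44, 44 and 36 for assumed rates of 0.95, 0.96, 0.965 and 0.97. At 0.96, 44 closures need at least 41 successes (level 0.022, power 0.902). The bracket plays no part in this figure.

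**Pass mark.** The lower bound is L(x, n) = the 0.025 quantile of Beta(x, n − x + 1), and the test passes if L > 0.81.

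- 68/75 = 90.7%: L = 0.817, pass
- 67/75 = 89.3%: L = 0.801, fail
- 67/74 = 90.5% (one failure removed): L = 0.815, pass
- 66/73 = 90.4% (one failure and one success removed from both counts): L = 0.812, pass

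So with 8 failures in 75, removing one of them reverses the conclusion.

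**Chance of passing when the true rate is 0.81.** With all 75 counted it is P(Bin(75, 0.81) ≥ 68) = 1.8%. With k closures removed, n = 75 − k and the pass marks are 67/74, 66/73 and 64/70.

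| How closures are removed | k = 1 | k = 2 | k = 5 |
|---|---|---|---|
| Worst case, k failures only: P(Bin(75, 0.81) ≥ 67, 66, 64) | 3.9% | 7.6% | 21.2% |
| Unrelated to outcome: P(Bin(75 − k, 0.81) ≥ 67, 66, 64) | 2.0% | 2.2% | 1.3% |
| k attempts are off-IFU and fail at the same 19% rate; only those that fail are dropped | 2.0% | 2.2% | 3.1% |

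In the worst-case row every success counted lies inside the denominator, so the row describes a calculation that could actually be run. The error comes from choosing removals by outcome. Removing closures without regard to outcome does not raise it above 2.5%.

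**The case against.** The strongest reply is that SAP 11.1 and 11.7 already settle the matter: the test is run on the mITT set, whose exceptions do not include departure from the IFU, so off-IFU failures stay in. The bracket also has an innocent reading, that it says which step of the IFU counts as a deployment attempt. The IFU is not among the documents, so neither reading can be confirmed. No section sets up an adherence review, and neither SAP 11.11 nor the deviations summary (Table 23) has an IFU category.

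Much of this stands. It rules out two stronger readings. A reader might infer that off-IFU successes remain in the numerator while leaving the denominator. SAP 11.7 does not allow that: a binomial numerator must lie within its denominator, and with two off-IFU attempts among 75 successes the ratio would be 75/73, for which no exact interval exists. A reader might also infer that the rate is in fact inflated. The documents give no off-IFU count, and with none the competing definitions agree on this point.

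The reply does not remove the conflict. SAP 11.7 names its endpoint the technical success rate, which is the term defined with the bracket in 4.2, and Table 4 reports it under that name. Nothing says which text prevails, and the wording in 9.3.1 and 11.10 is also unreconciled.

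**Conclusion.** The point holds as an inconsistency in a formally tested endpoint: an undefined qualifier in both definitions conflicts with the mITT set used for the test, and two more sections differ again. If the qualifier is used as a filter after outcomes are known, the tested rate can be inflated. It is not shown that it will be.

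The size depends on how removal happens. Near the pass mark one dropped failure is decisive. The false-positive chance of 3.9% to 21.2% assumes that every removed closure is a failure, 75 closures and a true rate of 0.81. It is an upper case and not an expected value. The endpoint is secondary and does not drive sample size. Correction before analysis is still worthwhile, because the performance claim rests on this rate.

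**What to change.** 1. Delete the bracketed reference to the IFU from SAP 4.2, item xiii, and from the protocol's definition.
2. Define the denominator once: every mITT closure in which the loading cannula was inserted into the Introducer sheath. This uses the SAP's own contact rule (9.3.1 footnote) and its own population (11.1).
3. Reconcile SAP 9.3.1 (non-deployments not due to device failure) and SAP 11.10 (implanted subjects) with that definition, so that each attempted closure has one stated place in the analysis.
4. If an IFU-adherent analysis is wanted, report it only as a labelled sensitivity analysis, with numerator and denominator both restricted and adherence judged without knowledge of outcome.

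The cost is a few words in two definitions, matching edits in two SAP sections and at most one table row. Sample size and conduct do not change. The reported success rate may be slightly less favourable.

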- Minimisation of the temporary disruption of arterial flow, which occurs with arterial clamping during surgical closure
- Reduction in scaring compared to surgical cut-down (as VCD use is percutaneous)

Schedule of Events

A schedule of study events is provided in Table 1 below as a guide. This is a tabular summary of the study activities and related scheduled procedures to be performed.

Table 1- Schedule of Study Events for Reference Only

Schedule of Events	Screening	Pre-Proc.	Peri- Proc.	Immed Post Proc.	Post Procedure			
					Approx. 30 mins post	Post 1hr	pre- discharg e	Follow-Up (1 & 3 Months)
Determine Eligibility	√	V	V					
Obtain Informed Consent	√							
Demographic Information	√							
Patient Medical History	√							
Physical Examination	√							
Laboratory Results (within 7 days pre-procedure)	V							
CT Angiogram (May be within 4 months pre-procedure)	√***		,				*	
Angiogram	√***		V	*			*	
Duplex Ultrasound				*	*	*	*	√ * *
Pulses		$\sqrt{}$		$\sqrt{}$	$\sqrt{}$		$\sqrt{}$	$\sqrt{}$
ABI	$\sqrt{}$							√****
Record procedure sheath size & details of graft/valve			$\sqrt{}$					
ACT before PerQseal® closure device insertion			$\sqrt{}$					
Estimate tissue tract depth								
Record PerQseal® details								
Time to deploy PerQseal® closure device			V					
PerQseal® device TTH			V					
Alternative therapy required			√					
PerQseal® device performance assessment				V				
Time from PerQseal® Introducer insertion to PerQseal® closure device deployment				V				
Overall procedural time								
Time to Ambulation					V	V		
Adverse Event Assessment			V		V	√		V

^{*}If Necessary, **3 month follow-up only otherwise if necessary, ***Either a CT Angiogram or Angiogram can be performed, **** at 1 month only if the patient has both dorsalis pedis and posterior tibial pulses absent in the ipsilateral leg.

Viva

DOC-DP2-68 CLINICAL INVESTIGATION PLAN SYNOPSIS FRONTIER IV REV AB

Definitions

Major Vascular Access Site Complication – In the context of this CIP and related to the femoral artery access site, major complications* are any of:

- Major vascular access site complications leading to death, life-threatening (BARC type 5) or major bleeding (BARC type 3a), visceral ischemia or neurological impairment; OR
- Distal embolization from the vascular access site requiring surgery or resulting in amputation or irreversible end-organ damage; OR

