4.2 Definitions of terms

- Pulse Grading System The peripheral pulse pressure shall be indicated using the following grading:
 - 0 Absent
 - 1 Diminished/weak
 - 2 Normal
 - 3 Strong
- ii. **Major Vascular Access Site Complication** In the context of this CIP and related to the femoral artery access site, major complications* are any of:
 - Major vascular access site complications leading to death, life-threatening (BARC type 5)
 or major bleeding (BARC type 3a), visceral ischemia or neurological impairment; OR
 - Distal embolization from the vascular access site requiring surgery or resulting in amputation or irreversible end-organ damage; OR
 - The use of unplanned endovascular or surgical intervention associated with access site related death, major bleeding (BARC type 3a), visceral ischemia or neurological impairment; ORleading to death, life-threatening or major bleeding*, visceral ischaemia or neurological impairment.

- Any access site related new ipsilateral lower extremity ischemia documented by patient symptoms, physical exam, and/or decreased or absent blood flow on lower extremity angiogram; OR
- Surgery for access site-related nerve injury; OR
- Permanent access site-related nerve injury; OR
- Access-site-related infection requiring intravenous antibiotics and/or extended hospitalization
- * Adapted from VARC-21.
- iii. **Minor Vascular Access Site Complications** In the context of this CIP and related to the femoral artery access site, minor complications* are any of:
 - Access site or access-related vascular injury
 - Dissection
 - Stenosis
 - Perforation
 - Rupture
 - > Arteriovenous fistula
 - Pseudoaneurysm (> 3 cm)
 - > Haematoma (> 6 cm)
 - Percutaneous closure device failure

not leading to death, life-threatening or major bleeding (BARC type 3a), visceral ischaemia or neurological impairment.

- Distal embolization from the vascular access site treated with embolectomy and/or thrombectomy and not resulting in amputation or irreversible end-organ damage.
- Localized access site infection treated with intramuscular or oral antibiotics.
- Any access site related unplanned endovascular stenting or unplanned surgical intervention not meeting the criteria for a major vascular complication.
- Access site related vascular repair or the need for vascular repair (via surgery, ultrasoundguided compression, transcatheter embolization, or stent graft)

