- xx. **Source Data Verification (SDV)** Evaluation of the conformity of the data presented in eCRFs with source data (medical records/notes, lab results, x-rays, etc.).
- xxi. **Ankle-brachial index (ABI)** The ratio of ankle systolic pressure to the arm systolic pressure, used in assessing the status of lower extremity arteries. It is calculated by dividing the higher of the left and right ankle pressures by the higher of the two brachial artery pressures.
- xxii. Time from PerQseal[®] Introducer insertion to PerQseal[®] closure device deployment defined as the time from insertion of the PerQseal[®] Introducer to complete removal of the PerQseal[®] closure device and Introducer-sheath from the patient following deployment.

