9.3 Study population

Patients will not be excluded on the basis of age, race, concomitant therapy or co-existing disease. Each centre will continue to enrol eligible patients until a minimum combined Clinical Investigation population of 75 patients is achieved.

Patients with bilateral percutaneous access in the common femoral arteries where both arteries meet all eligibility criteria may, at the discretion of the investigator, both be closed with the PerQseal® closure device. If a PerQseal® is used on the contralateral femoral artery then this will be treated as an independent closure i.e. each limb will be counted as a separate closure only for the purposes of Performance Analysis.

Consented patients who receive contact with the PerQseal[®] closure device become an enrolled subject.

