9.3.3 Exclusion criteria

General Exclusion Criteria:

- Severe acute non-cardiac systemic disease or terminal illness with a life expectancy of less than six months.
- ii. Evidence of systemic bacterial or cutaneous infection, including groin infection.
- iii. Known bleeding diathesis, definite or potential coagulopathy, platelet count < 100,000/µl or patients on long term anticoagulants with an INR greater than 1.2 at time of procedure or known type II heparin-induced thrombocytopenia.
- iv. Severe; claudication or peripheral vascular disease (e.g. Rutherford category 3 or greater or ABI < 0.5), documented untreated iliac artery diameter stenosis > 50% or previous bypass surgery/stent placement in the common femoral artery of ipsilateral limb.
- v. Known allergy to any of the materials used in the PerQseal® (refer to Instructions for Use).
- vi. Subject has undergone a percutaneous procedure using a non-absorbable vascular closure device (excluding suture mediated) for haemostasis in the ipsilateral target leg.
- vii. Patients that have undergone a percutaneous procedure in the ipsilateral leg, within the previous 30 days.
- viii. Patients that have undergone a percutaneous procedure using an absorbable intravascular closure device for haemostasis, in the ipsilateral leg, within the previous 90 days.
- ix. Evidence of arterial diameter stenosis > 20% or anterior or circumferential calcification within 20 mm proximal or distal to target arteriotomy site based on pre-procedure CT angiography.
- x. Females who are pregnant or lactating or in fertile period not taking adequate contraceptives. A pregnancy test may be performed.
- xi. Patients that have a lower extremity amputation from the ipsilateral or contralateral limb.

Procedural Exclusion Criteria*:

- xii. Arterial access other than common femoral artery obtained for ipsilateral target leg.
- xiii. Subject has a tissue tract expected to be greater than 10 cm.
- xiv. Use of thrombolytic agents within 24 hours prior to or during the endovascular procedure which causes fibrinogen < 100 mg/dl.
- xv. Significant blood loss/transfusion (defined as requiring transfusion of 4 or more units of blood products) during index procedure or within 30 days prior to index procedure.
- xvi. Activated clotting time (ACT) > 350 seconds immediately prior to sheath removal or if ACT measurements are expected to be > 350 seconds for more than 24 hours after index procedure.

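### The SAP defines ABI as one best-leg value per patient, which contradicts the left and right columns of Table 17 and does not fit the ipsilateral trigger for the 1-month ABI

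*SAP*

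**What the plan says.** SAP 4.2 item xxi describes ABI as a ratio of ankle to arm systolic pressure, "used in assessing the status of lower extremity arteries", and says that it is "calculated by dividing the higher of the left and right ankle pressures by the higher of the two brachial artery pressures". Neither document gives any other ABI formula or a rule for choosing a leg.

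ABI is used in three places:

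- **SAP 16.1, Table 17.** The shell has separate left and right columns at baseline and at 3 months, each with N, mean, median, SD, IQR, minimum and maximum. There is no 1-month column.
- **Protocol Table 1.** ABI is scheduled at screening and at follow-up. The footnote restricts it: "at 1 month only if the patient has both dorsalis pedis and posterior tibial pulses absent in the ipsilateral leg".
- **Exclusion iv (protocol, and SAP 9.3.3).** ABI appears as an example of severe disease: "Severe; claudication or peripheral vascular disease (e.g. Rutherford category 3 or greater or ABI < 0.5". The criterion ends with a reference to the ipsilateral limb, but the ABI example itself names no leg.

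The ischaemia component of the primary endpoint (SAP 4.2 item ii, and the protocol's definitions) is worded without ABI: "new ipsilateral lower extremity ischemia documented by patient symptoms, physical exam, and/or decreased or absent blood flow on lower extremity angiogram".

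**The concern.** A maximum over the two ankles discards the worse leg. The places that use ABI either report it by leg or call for it because of a finding in one leg, so the defined quantity does not match its planned use. A programmer could not follow both the definition and Table 17: one of them would have to be ignored, and the plan does not say which.

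What is at stake is the credibility of the ABI summaries. The study device leaves components inside the artery, and a follow-up ABI that looks normal would be read as reassurance about the treated leg. Under the stated formula that value may come wholly from the leg that was not treated. Where both groins are closed with the device, a single value cannot be attributed to either limb.

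**Working it through.** The documents state no ABI figure to reproduce and give no pressures. All pressures below are assumptions chosen to show how the formula behaves.

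**Notation.** T is the treated-leg ankle pressure, C the other ankle, and B the higher brachial pressure.

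- SAP formula (4.2 item xxi): ABI = max(T, C) / B
- Per-leg formula: ABI of the treated leg = T / B

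**1. Table 17.** The formula does not distinguish left from right. Each visit yields one value, so the two columns would be identical.

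**2. Single illustration.** T = 60, C = 130, B = 140 mmHg.

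- SAP formula: 130/140 = 0.93
- Treated leg: 60/140 = 0.43

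**3. Treated leg starts equal to the other.** B = 130 and C = 135 are held fixed while T falls from 135.

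| T (mmHg) | SAP ABI | Treated-leg ABI |
|---|---|---|
| 135 | 1.04 | 1.04 |
| 120 | 1.04 | 0.92 |
| 100 | 1.04 | 0.77 |
| 80 | 1.04 | 0.62 |
| 64 | 1.04 | 0.49 |
| 50 | 1.04 | 0.38 |
| 30 | 1.04 | 0.23 |
| 0 | 1.04 | 0.00 |

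The SAP value is 135/130 = 1.04 throughout, so the fall is fully hidden. The same holds for any start with T at or below C.

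**4. Treated leg starts higher than the other.** B = 130, C = 110, and T falls from 135 to 60.

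- SAP formula: 135/130 = 1.04, then 110/130 = 0.85, a fall of 25/130 = 0.19
- Treated leg: 135/130 = 1.04, then 60/130 = 0.46, a fall of 75/130 = 0.58

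Here the ABI does move, but only until T reaches C. Of the 75 mmHg fall, 25 mmHg shows and 50 mmHg does not.

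**5. Exclusion iv.** max(T, C)/B is below 0.5 only if both T/B and C/B are below 0.5. Under the SAP formula, the ABI example is therefore met only when both legs are below the cut-off. In step 3, a treated leg at 64 mmHg (0.49) is below it and the SAP value is not.

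**6. The 1-month ABI.** It is called for because both pedal pulses are absent in the ipsilateral leg. If the other leg has the higher pressure, the value obtained describes that other leg. Table 17 has no place to report it in any case.

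**The case against.** The strongest reply is that this is a wording slip with little consequence. Table 17 already shows that per-leg values are intended, and sites may well record them. ABI is not among the study variables in SAP 11.5 and plays no part in the analyses in 11.6 to 11.9; its only planned output is a descriptive table. SAP section 16 allows minor changes to table shells without revising the SAP, so the missing 1-month column is easily repaired.

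Most of this stands as a limit on the consequences. It does not remove the contradiction, because the only formula given is the best-leg one and nothing available says that sites depart from it.

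Two stronger readings are tempting, and the documents do not support them:

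- **That new ischaemia in the treated leg would escape the primary endpoint.** That criterion rests on symptoms, examination and/or angiogram. Table 18 reports pedal pulses by leg at seven time points up to 3 months, and duplex ultrasound is scheduled at 3 months. The 1-month ABI is taken only after examination has already flagged the leg, and a normal best-leg ABI does not undo that finding. A fall may be hidden on ABI without being missed by the trial.
- **That patients with a severely diseased target leg would be enrolled.** ABI is one example within exclusion iv, beside Rutherford category and untreated iliac stenosis. Exclusion ix separately covers stenosis and calcification near the target site. The public protocol is a synopsis without an ABI formula, so how sites calculate ABI at screening cannot be seen.

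Nor is it true in general that a fall is invisible while the other leg is normal: step 4 of the working is a counter-example.

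**Conclusion.** The definition contradicts Table 17 and does not fit the ipsilateral trigger for the 1-month ABI. This rests on the text alone and needs no assumed figure.

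The size of the masking does depend on assumed pressures. It is complete when the treated leg starts equal to or lower than the other (1.04 throughout, against a treated-leg value falling to 0.00). When the treated leg starts higher, it is partial once that leg drops below the other (1.04 to 0.85, against 1.04 to 0.46). These comparisons hold the other ankle and the brachial pressure constant.

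The effect is confined to the ABI summaries and, if screening uses the SAP formula, to the ABI example in exclusion iv. The point should be corrected before the tables are programmed.

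**What to change.** - In SAP 4.2 item xxi, define ABI per leg, as that leg's ankle pressure over the higher of the two brachial pressures, and use this for Table 17 and for follow-up.
- Add the conditional 1-month ABI to Table 17, with its own N, since only patients meeting the pulse condition will have a value.
- Reconcile SAP 4.2 item xxi, Table 17, the footnote to protocol Table 1 and exclusion iv, so that exclusion iv states which leg's ABI it means. That choice belongs to the sponsor.

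The cost is one definition, one set of table columns and one clarifying phrase. The current formula already requires both ankle pressures, so no further measurement is needed.
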